## 3. Methods

### 3.1 Study design, population and procedures

Study design: open randomized controlled prospective cross over cohort study

Study population: A) group of 10 novices, B) group of 10 surgical, urological or gynaecological residents, C) group of 10 experts consisting of surgeons, urologists or gynaecologists.

Study procedure: After information is given on the purpose and set up of the experiment all participants will be asked to sign an informed consent form.

A video will be shown of the working of a normal VN and of the VN+. After this a detailed video will be shown wherein all basic steps of the procedure are outlined. Then after randomization half of the group will start with a VN and the other half with the VN+. After 5 attempts the groups will switch device and repeat the procedure.

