### 3.2 Procedure and anatomical considerations

After making a small skin incision the insertion of the Veress needles will be:

- at Palmer's point which is 2-3 cm below the left costal margin in the midclavicular line.
- right below the umbilicus after lifting the skin with a clamp

A "grid" will be drawn on the skin. Guided by the grid each attempt will be in a new and unused part of the abdominal wall.

As in total 300 VN(+) insertions have to be performed we will probably need three cadavers

The anatomical region to be used will thus be the abdomen.

In order to see what depth the different needles reach and the possible anatomical structures that will be injured, we will first introduce a laparoscope in the left (or depending on the cadaver the right) lower abdominal quadrant via an open technique and establish pneumoperitoneum through this laparoscope trocar with a pressure that is as low as possible.

Then measurements will take place through recording the number of marks on the needle (previously laser engraved) that are to be seen in the abdomen. The actions will all be filmed and photographed.

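### The design does not block on cadaver, and the primary test ignores participant and cadaver, so differences between bodies can enter the VN versus VN+ contrast.

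*Combined protocol and SAP*

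**What the plan says.** Section 3.1 calls the study an "open randomized controlled prospective cross over cohort study" and enrols "A) group of 10 novices, B) group of 10 surgical, urological or gynaecological residents, C) group of 10 experts". On the order of needles it says "half of the group will start with a VN and the other half with the VN"+, and then "After 5 attempts the groups will switch device and repeat the procedure".

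Section 3.2 gives the volume and the number of bodies: for 300 insertions in total, "we will probably need three cadavers". Its only rule on where an insertion goes is "Guided by the grid each attempt will be in a new and unused part of the abdominal wall". It also lets the side of laparoscope entry depend on the cadaver, so the plan recognises that bodies differ.

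Section 4 compares insertion depth between the two needles with a Mann-Whitney test, which treats the two sets of measurements as independent. It has no term for participant or cadaver. The limitations in section 6 contrast cadaveric with living tissue and do not mention differences from one cadaver to another.

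No section says which body a participant uses, that both blocks share a body, that both needles are used equally on each body, or that the cadaver is recorded for each insertion.

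**The concern.** The primary objective in section 2 is the amount of benefit of the VN+ over the standard needle, so the study must estimate a difference in depth. A crossover removes from that difference whatever stays the same across a participant's two blocks. The operator stays the same. The body stays the same only if the schedule keeps it so, and the plan is silent on this.

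Abdominal walls may differ in thickness and resistance, and with about three bodies such differences cannot be relied on to average out. If a participant's blocks fall on different bodies, the measured needle difference includes a body difference. The harm depends on the pattern: lost precision if bodies are used haphazardly, little bias if the body changes with period, and confounding if each needle tends to stay with particular bodies. Full confounding could not be repaired in the analysis, so the point has to be settled before data collection.

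The unpaired test is part of the same gap. It does not use the within-participant comparison that the crossover was set up to provide, and so it would not reap the gain from keeping both blocks on one body.

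**Working it through.** **Inputs from the documents.** 3 groups of 10 participants, 2 needles and 5 attempts per needle (section 3.1); 300 insertions and probably 3 bodies (section 3.2); Mann-Whitney test at 0.05 (section 4).

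**Assumptions, because the documents give no SDs.** SD of a participant's VN minus VN+ difference on one body: 5 mm. Between-cadaver SD of depth, s: 3, 5 or 8 mm.

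**1. The plan's count.** 3 × 10 × 2 × 5 = 300, which agrees with section 3.2. Over three bodies this is 300/3 = 100 insertions each. At 10 insertions per participant, that is 10 participants per body. Each needle has 150 insertions.

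**2. Both blocks on one body.** The cadaver effect subtracts out. SE = 5/√30 = 0.91 mm, whatever s is.

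**3. Haphazard use of three bodies.** If each block's body is drawn at random, the two blocks differ in body with probability 2/3, and the variance of each paired difference becomes 25 + (2/3) × 2s².

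| s (mm) | Variance | SE = √(variance/30) (mm) | Variance ratio to 25 |
|---|---|---|---|
| 3 | 37.0 | 1.11 | 1.48 |
| 5 | 58.3 | 1.39 | 2.33 |
| 8 | 110.3 | 1.92 | 4.41 |

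These figures apply to a paired analysis, which the plan does not yet have.

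**4. Body follows period, order balanced.** If block 1 is on body A and block 2 on body B, half the participants carry +(A−B) in their VN minus VN+ difference and half carry −(A−B). The body term cancels in the mean. It still widens the spread of the paired differences, so a simple paired test becomes conservative rather than biased.

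**5. Needles tied to bodies.**
- One body per needle: the bias is A−B, with SD √2 × s = 1.41s, or 4.2, 7.1 or 11.3 mm. This needs 150 insertions on each of two bodies.
- Three equally loaded bodies: with 100 per body and 150 per needle, at least one body must carry both needles. Take VN as 100 on A and 50 on B, and VN+ as 50 on B and 100 on C. The bias is (2/3)A + (1/3)B − (1/3)B − (2/3)C = (2/3)(A−C). Its SD is (2/3) × √2 × s = 0.94s, or 2.8, 4.7 or 7.5 mm.

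With the bodies fixed, neither bias shrinks as insertions are added.

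**6. Behaviour of the planned test.** A simulation with no true needle effect (2,000 runs per scenario) used attempt SD 1, participant SD 0.5 or 1, and cadaver SD 0.25, 0.5 or 1, all in units of the attempt SD. It pooled 150 against 150 insertions. The table shows false-positive rates at 0.05; ranges run over the two participant SDs.

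| Use of bodies | Test | Cadaver SD 0.25 | 0.5 | 1.0 |
|---|---|---|---|---|
| Same body | Mann-Whitney | 0.6–2.7% | 0.7–1.9% | 0.3–1.3% |
| Same body | Paired | 5.2–5.4% | 5.3–5.4% | 5.0–5.2% |
| Haphazard | Mann-Whitney | 1.1–4.2% | 3.8–8.7% | 10.7–16.0% |
| Haphazard | Paired | 4.9–5.0% | 5.0–5.4% | 4.4–4.8% |
| Body follows period | Paired | 2.8–3.6% | 1.8% | 1.1–1.3% |
| One body per needle | Mann-Whitney | 39–50% | 65–73% | 82–87% |
| One body per needle | Paired | 54–55% | 75% | 87–88% |

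Even with the same body for both blocks, the planned test falls well below its nominal 5%, because it sets the needle difference against variation between participants and bodies. A paired test holds 5% under same-body and haphazard use. Neither test is protected when each needle has its own body.

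**The case against.** The best reply is that this is silence, and that the nearest text leans towards same-body use. Section 3.1 says "After 5 attempts the groups will switch device and repeat the procedure": the needle changes, and no change of body or station is mentioned. The cadaver count in section 3.2 reads as a capacity calculation, and ten participants fit on one body. If bodies were used one after another as the grid filled, few participants would be split. All of this stands. It makes same-body use the likelier intention, but it does not make it a rule.

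A reader might infer more: that the study runs one needle per cadaver, or that the crossover loses its main advantage. The documents support neither. They describe no stations. Control for the operator survives whichever body is used, which matters when novices, residents and experts are mixed; only control for the body is at risk. Complete confounding needs one body per needle, while section 3.2 expects three bodies. With three equally loaded bodies the bias is one third smaller, and the shared body would allow a within-body check if the cadaver were recorded. Balanced order also makes one plausible pattern, a change of body with period, nearly harmless for bias.

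It is also fair to say that the precision figures presuppose a paired analysis, and that at the two smaller cadaver SDs in the simulation haphazard use takes the planned test to at most about 9% false positives. Both points stand. They are why the scheduling rule and the change of test belong together.

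**Conclusion.** The point holds as a gap in the plan, not as a demonstrated bias. The schedule neither keeps a participant's two blocks on one body nor balances needles within bodies, and the planned test uses neither participant nor cadaver.

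The consequence ranges from none (same body throughout), through a loss of precision (variance 1.48 to 4.41 times larger in a paired analysis under haphazard use), to partial or full confounding if needles are tied to bodies (bias SD 0.94 or 1.41 times the cadaver SD). Which of these applies cannot be told from the documents. The millimetre figures rest on assumed SDs, and the 8 mm case, where bodies vary more than the 5 mm paired difference, drives the largest of them.

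The change should be made before the first insertion. It costs almost nothing, it protects the primary contrast, and confounding by body could not be undone afterwards.

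**What to change.** In sections 3.1 and 3.2, add: *Each participant makes all ten insertions (five VN, five VN+) on one cadaver. The starting needle is balanced within each experience group and, as nearly as possible, within each cadaver. The cadaver number is recorded for every insertion.* Spread the experience groups over the bodies when scheduling; one group per body would satisfy the rule but would confound the comparison of groups with body.

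In section 4, replace the unpaired Mann-Whitney test with a within-participant comparison. One option is a Wilcoxon signed-rank test on each participant's VN minus VN+ summary depth, which keeps the non-parametric approach. Another is a mixed model for the individual insertions, with participant and cadaver included.

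The cost is slightly less scheduling freedom, including the option of running one needle per station, and one extra data column. No additional participants, cadavers or insertions are needed.

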## 2. Study objective(s):

The purpose of the study is to repeat our previous ex-vivo experiments in a real-life laparoscopic set up in a human/cadaveric model.

The primary objective will be to establish what the amount of benefit will be in using the VN+ as compared to a standard VN. We need to measure in a life-like situation what the reduction of the overshoot will be while in the hands of novices, junior residents and experts to validate the learning curve. Other secondary objectives are establishing the amount of haptic feedback of the VN+ compared to the standard VN and potential safety issues. All the practical investigations will need to take place in the ASC. Data study and technical alterations on the instruments will take place at the TU Delft.

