#### 4. Data collection and analysis

In all three groups the measured maximum insertion depths will be calculated in Excel and then any differences between the conventional (VN) and the modified (VN+) groups will be determined with a Mann-Whitney test (SPSS v16, SPSS inc. Chicago, IL) as the data will not be normally distributed. A p-value<0.05 will be considered significant.

All inadvertent tissue or organ damage will be determined and compared between the two types of needles and the groups using a Student T-test (SPSS v16, SPSS inc. Chicago, IL).

A questionnaire (with a Likert scale) will be used to establish the amount of haptic feedback the subjects experience with either the VN or the VN+ at the two different entry sites.

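### Counting only the needle marks seen in the abdomen scores an insertion too shallow whenever the tip is hidden in or behind tissue

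*Combined protocol and SAP*

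**What the plan says.** Section 2 makes the amount of benefit the primary objective: "We need to measure in a life-like situation what the reduction of the overshoot will be". Section 3.2 places a laparoscope through a lower quadrant and creates a pneumoperitoneum "with a pressure that is as low as possible". The stated purpose of the view is double: "In order to see what depth the different needles reach and the possible anatomical structures that will be injured". The depth reading is then taken by "recording the number of marks on the needle (previously laser engraved) that are to be seen in the abdomen". The same section adds: "The actions will all be filmed and photographed".

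Section 4 carries the readings into the analysis: "the measured maximum insertion depths will be calculated in Excel", and differences between the needles "will be determined with a Mann-Whitney test". Injury is a separate outcome: "All inadvertent tissue or organ damage will be determined and compared between the two types of needles".

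No section says whether the marks are numbered or how far apart they are. None says how to score an attempt whose tip cannot be seen. The limitations in section 6 mention the pneumoperitoneum but not hidden marks.

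**The concern.** A count of visible marks equals the length inside the cavity only while the whole intra-abdominal part of the needle is in view. Once the tip is inside bowel or omentum, or behind a fold of tissue, the marks nearest the tip disappear and the count stops at the tissue surface. A needle that just touches the bowel and one that lies 20 mm inside it then receive the same score.

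Such attempts are the ones the new needle is meant to prevent. If the device works as its developers expect, they occur mainly with the standard needle, so most of the lost length is lost from the standard arm and the estimated reduction in overshoot comes out too small. The injury outcome does not repair this, because it is analysed separately and adds nothing back to the depth score.

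**Working it through.** **Design count.** 3 groups × 10 participants × 2 devices × 5 attempts = 300 insertions, 150 per device. This reproduces the 300 stated in section 3.2. The plan gives no depth, standard deviation, gap or frequency of hidden tips, so everything below is an illustration on assumed values.

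**What the rule records.** Let d be the true length inside the cavity and g the gap from the inner abdominal wall to the tissue in the needle's path.
- Tip in view, at any depth: recorded depth = d.
- Tip hidden: recorded depth = g, so the error is −(d − g).

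The error is never positive, and it occurs only in hidden-tip attempts.

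**Assumed inputs.** Depth with the standard needle: mean 30 mm, SD 12. Depth with VN+: mean 18 mm, SD 8. Both are normal, floored at zero, which makes the true difference 11.99 mm. Gaps are 40, 30 and 20 mm. Let q be the share of insertions deeper than g whose tip is hidden; q = 0.25, 0.5 or 1.

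**Formula.** Mean excess beyond the gap: E(g) = s·φ(z) + (m − g)·Φ(z), with z = (m − g)/s. Measured difference = 11.99 − q × [E for VN − E for VN+].

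| Gap | Share deeper than gap, VN / VN+ | E, VN | E, VN+ | Difference in E |
|---|---|---|---|---|
| 40 mm | 20% / 0.3% | 1.36 | 0.01 | 1.35 |
| 30 mm | 50% / 7% | 4.79 | 0.23 | 4.55 |
| 20 mm | 80% / 40% | 11.36 | 2.29 | 9.07 |

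(Differences are taken before rounding.) For example, with a 30 mm gap and q = 0.25: 11.99 − 0.25 × 4.55 = 10.9 mm.

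| Gap | q = 0.25 | q = 0.5 | q = 1 (worst case) |
|---|---|---|---|
| 40 mm | 11.7 mm (3% lost) | 11.3 mm (6%) | 10.6 mm (11%) |
| 30 mm | 10.9 mm (9%) | 9.7 mm (19%) | 7.4 mm (38%) |
| 20 mm | 9.7 mm (19%) | 7.5 mm (38%) | 2.9 mm (76%) |

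A simulation with 2,000,000 draws per device agrees with these figures to 0.1 mm.

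**Effect on the planned test.** The Mann-Whitney test responds to the probability that a standard-needle insertion is deeper than a VN+ insertion, ties counting half. With no hidden tips this is Φ(12/√(12² + 8²)) = Φ(0.83) = 0.80. With q = 0.25 it is 0.80, 0.79 and 0.76 at gaps of 40, 30 and 20 mm. With q = 1 it is 0.80, 0.79 and 0.70.

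**Sensitivity to the depth assumptions.** With log-normal depths (VN mean 40 mm, SD 15; VN+ mean 25 mm, SD 10; simulated true difference 14.9 mm), the measured difference at gaps of 40, 30 and 20 mm is 13.7, 12.6 and 11.6 mm for q = 0.25, and 9.9, 5.6 and 1.4 mm for q = 1. The probability falls from 0.82 to between 0.81 and 0.66. The pattern is the same: always shrinkage, by very different amounts.

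**The case against.** The plan may intend more than it writes. The marks might be distinguishable, and with every attempt on film a reader could identify the mark at the abdominal wall and obtain the full length even with the tip out of sight. That would solve the problem, but the written rule is a count of visible marks. Film cannot show marks inside an organ, and identical marks cannot be converted to depth when the tip is hidden.

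The gap need not be small. Low gas pressure limits it, but at the umbilical site the skin is lifted with a clamp, and section 6 says the pneumoperitoneum is there so that depth can be read. This stands: the documents fix no pressure and no clearance, so neither a small nor a generous gap can be presumed.

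A reader might infer that all the worst overshoots are mis-scored, or that most of the benefit would disappear. Neither follows. A deep insertion into free space, or one that pushes tissue aside and stays in view, is scored correctly. The 76% loss requires every insertion beyond a 20 mm gap to be hidden, which on the assumed depths means 80% of standard-needle and 40% of VN+ attempts. Nothing in the documents supports such rates.

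Finally, if the standard needle overshoots more, the error works against the new device. It would understate a benefit and could not create one, and the rank test may well remain significant. This also stands, but section 2 asks for the amount of benefit, and that is the quantity distorted.

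**Conclusion.** The concern holds for attempts in which the tip is inside or behind tissue when the reading is taken. Followed literally, the rule in section 3.2 under-reads those attempts, and nothing else in the plan corrects them. The bias in the measured reduction is toward zero on the condition that hidden tips are more frequent, or lie deeper, with the standard needle, as the study's own hypothesis implies.

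Its size is unknown. On the normal-depth assumptions the loss is 3% to 19% if a quarter of the insertions beyond the gap are hidden, and 11% to 76% in the limiting case where all are. The rank comparison is less sensitive, falling from 0.80 to no lower than 0.70. The documents do not support a claim that the comparison is invalid, or that it favours the new needle. This is a stated measurement rule for which a better one is readily available.

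**What to change.** In section 3.2, define depth as the distance from the tip to the mark lying at the inner (peritoneal) surface of the abdominal wall, using marks identifiable by their distance from the tip or from the hub. That single reading gives the full intra-abdominal length whether or not the tip can be seen.

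Record for each attempt whether the tip was hidden. Where the wall mark cannot be identified, enter the visible length as a lower bound (at least x mm), and state in section 4 that such values will be ranked or analysed as censored.

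Do not substitute the marks left outside the skin unless wall thickness at that site is also known. That length includes the abdominal wall, whose thickness can differ by cadaver, site and clamp lift.

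Cost: a few sentences and one extra data column, with no additional insertions, cadavers or staff. The downside is that section 3.2 describes the needles as already engraved; if the existing marks cannot be told apart, they must be coded or re-engraved before use. This has to be settled before the first insertion, because length hidden behind indistinguishable marks cannot be recovered later from the images. Label: cheap improvement.

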#### 4. Data collection and analysis

In all three groups the measured maximum insertion depths will be calculated in Excel and then any differences between the conventional (VN) and the modified (VN+) groups will be determined with a Mann-Whitney test (SPSS v16, SPSS inc. Chicago, IL) as the data will not be normally distributed. A p-value<0.05 will be considered significant.

All inadvertent tissue or organ damage will be determined and compared between the two types of needles and the groups using a Student T-test (SPSS v16, SPSS inc. Chicago, IL).

A questionnaire (with a Likert scale) will be used to establish the amount of haptic feedback the subjects experience with either the VN or the VN+ at the two different entry sites.

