## 1. Background and significance

Complications that occur in laparoscopic surgery are often associated with the initial entry into the peritoneal cavity. The literature reported incidences of Veress Needle (VN) injuries of e.g. 0.31% and 0.23%. In a 2010 national survey of laparoscopic entry techniques in the Canadian General Surgical practice, 57.3% of respondents had either experienced or witnessed a serious laparoscopic entry complication like bowel perforation and vascular injury. As those complications are potentially life threatening and should be avoided at all costs, improving safety of this initial action is paramount.

Based on a bare minimum design approach with focus on function expansion of existing components, a new Safety mechanism was developed for the VN that decreases the risks of VN overshooting. The mechanism works by preventing the puncturing acceleration of the tip of the VN by decoupling the surgeon's hand from the VN immediately after entering the abdomen.

A first prototype of our so called VN+ with force decoupling mechanism proved very reliable in reducing overshooting in an ex-vivo model.

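### The primary depth comparison applies an unpaired Mann-Whitney test to crossover data with five insertions per needle from every participant, so its 5% level is not assured

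*Combined protocol and SAP*

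**What the plan says.** Section 3.1 describes the design in these words: "Study design: open randomized controlled prospective cross over cohort study". It has three groups of 10 (novices, residents, experts). On start order it says: "Then after randomization half of the group will start with a VN and the other half with the VN" (the modified needle, VN+). It continues: "After 5 attempts the groups will switch device and repeat the procedure". Section 3.2 adds: "As in total 300 VN(+) insertions have to be performed we will probably need three cadavers". It names two entry sites.

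Section 2 makes the benefit of VN+ over VN the primary objective, with the reduction in overshoot to be measured "while in the hands of novices, junior residents and experts to validate the learning curve".

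For depth, Section 4 gives one test: "any differences between the conventional (VN) and the modified (VN+) groups will be determined with a Mann-Whitney test". The reason offered is "as the data will not be normally distributed", and p<0.05 counts as significant. The variable is the maximum insertion depth. Nothing in the document mentions pairing, a unit of analysis, or how the five attempts per needle are to be combined.

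**The concern.** A Mann-Whitney test needs two independent samples of independent observations. Here the same people supply both samples, with five depths each. Non-normality is a reason to use ranks; it is not a reason to drop the pairing.

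The choice of unit does not rescue the test. If every insertion is entered, both the pairing and the clustering within participants are ignored. If one value per participant and needle is entered, the pairing is still ignored. The word for groups in Section 4 cannot mean separate people for each needle, because Section 3.1 has everyone use both.

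This is the only test given for the primary objective. If its level depends on quantities that the plan neither states nor models, neither a significant nor a non-significant result can be read at face value.

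**Working it through.** **Step 1: the plan's own count.** 3 groups x 10 = 30 participants (Section 3.1). 30 x 2 needles x 5 attempts = 300 insertions, as Section 3.2 states. The two entry sites do not multiply this count. The planned test is therefore 50 v 50 per group or 150 v 150 overall if insertions are entered, and 10 v 10 or 30 v 30 if participants are.

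**Step 2: variance with all insertions entered.** The document gives no SD, correlation, effect size or power, so the inputs from here on are assumptions. Set the variance of one depth to 1 = u + v + e, where u is the stable participant share, v the participant-by-needle share and e the insertion-level remainder. For one group of 10:

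- true variance of the device difference: 2(v + e/5)/10
- variance that a pooled two-sample test assumes: 2(u + v + e)/50 = 2/50
- ratio: 5v + e = 1 + 4v - u

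The test is conservative when the ratio is below 1 and liberal when it is above 1. Break-even is v = u/4. The approximate true level is 2[1 - Φ(1.96/√ratio)].

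| u | v | ratio | approximate level | simulated level, 50 v 50 |
|---|---|---|---|---|
| 0.6 | 0 | 0.4 | 0.2% | 0.6% |
| 0.4 | 0 | 0.6 | 1.1% | 1.7% |
| 0.2 | 0.05 | 1.0 | 5.0% | 5.3% |
| 0.2 | 0.1 | 1.2 | 7.4% | 7.6% |
| 0.1 | 0.2 | 1.7 | 13.3% | 13.0% |

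The simulation used 20,000 runs with no device effect and no period shift, two-sided 5%. With skewed integer counts the range was 0.4% to 13.7%. A separate simulation of 150 v 150 with skewed depths and other variance shares gave 0.6% to 17.4%.

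**Step 3: one mean per participant and needle, still unpaired.** The ratio becomes (v + e/5)/(u + v + e/5), which never exceeds 1. At u=0.4, v=0, e=0.6 it is 0.12/0.52 = 0.23. Simulated level for 10 v 10: 4.0% to 4.3% at u=0, and 0.0% to 2.4% for u from 0.1 to 0.6.

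**Step 4: power in one group at a 0.5 SD effect, using participant means.** The period-adjusted test is a rank-sum comparison of period 1 minus period 2 differences between the two start orders, assumed 5 v 5.

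| u, v, period shift | pooled 50 v 50 | unpaired 10 v 10 | signed-rank | period-adjusted |
|---|---|---|---|---|
| 0.4, 0, none | 74% | 20% | 81% | 70% |
| 0.4, 0.1, none | 68% | 17% | 58% | 46% |
| 0.1, 0.2, none | 65% (at 13% error) | 30% | 39% | 29% |
| 0, 0, none | 67% | 60% | 58% | 46% |
| 0.4, 0, 0.5 SD | 70% | 12% | 44% | 69% |

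The level of the signed-rank test is 4.4% to 5.1% without a period shift and 0.2% to 2.6% with the 0.5 SD shift. The period-adjusted test stays at 2.8% to 3.5% either way. At u=0.4, v=0 and a 0.2 SD shift, signed-rank is still ahead (73% v 69%); the two are about equal near 0.3 SD.

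**Step 5: all 30 participants, 0.5 SD, no period shift.** At (u, v) = (0.4, 0), (0.4, 0.1) and (0.1, 0.2), pooled power is 99.8%, 99% and 96%, at true levels of 1.3%, 5.4% and 12.3%. Unpaired 30 v 30 gives 88%, 77% and 82%; signed-rank gives 100%, 98% and 88%.

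Entry site and cadaver were not modelled.

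**The case against.** The strongest reply is that the harm may be small. Where stable participant differences dominate, the pooled test is conservative, so a positive result would be safe. At 1 SD in one group its power is 98% to 100%, and even unpaired 10 v 10 reaches 77% to 99%. No patients are treated. All of this stands as a limit on the consequences. It does not make the test fit the design, and a large effect cannot be presumed: Section 1 says that the first prototype "proved very reliable in reducing overshooting in an ex-vivo model" but gives no size.

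A second reply is that the maximum insertion depth in Section 4 could itself be the rule for combining attempts, namely the largest of five. More probably it means the deepest point of each insertion. Under either reading the test stays unpaired. The figures would change, however: with a per-participant maximum (u=0.4, v=0, 0.5 SD, one group), signed-rank power falls to about 46% and period-adjusted to about 36%. The wording therefore needs to be settled.

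Third, a within-participant test is not better in every respect. In single groups it can have less nominal power than the pooled test. It can also react more strongly to unequal carry-over. Both points are correct and are listed as downsides under the fix.

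A reader might infer that the planned test inflates false positives. The document does not support that: inflation needs v above u/4, and nothing in it shows this.

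**Conclusion.** The concern holds: the primary test does not match the crossover with repeated insertions, and its 5% level is not assured under any reading of the unit of analysis. That conclusion needs no assumed numbers. The size does. Across the assumed shares, the pooled test within one group runs from about 0.6% to 13%, and the unpaired test on participant means is conservative once participants differ. The simulations assume equal numbers per start order within each group, a balance that Section 3.1 does not clearly state: half of the group may mean half of all 30.

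Two further inferences go beyond the document. One is that the trial's conclusion will be wrong; with a large effect, the choice of test may not matter. The other is that only a period-adjusted test will do. The learning curve in Section 2 is a comparison across experience levels and does not itself establish a shift between a participant's first and second period. The choice between the two within-participant tests is a trade-off that depends on an unknown period effect.

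**What to change.** In Section 4, replace the Mann-Whitney comparison of VN with VN+ by a within-participant analysis:

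1. State that maximum insertion depth is the deepest point of each insertion, if that is what is meant.
2. Reduce the five attempts per needle to one pre-specified summary per participant. The mean has more power than the maximum or the median (median, u=0.4, v=0, one group: signed-rank 65% instead of 81%, period-adjusted 54% instead of 70%).
3. Test the participant differences over all 30 and then per experience group, with a Hodges-Lehmann estimate and 95% confidence interval.
4. Choose one test before analysis. Signed-rank has more power if the period effect is small; the rank-sum comparison of period differences between start orders keeps its power if there is one.
5. Specify in Section 3.1 whether start order is balanced within each experience group. Stratify the sequence comparison by group only if it is.
6. In Section 3.2, record entry site and cadaver for each attempt. Five attempts cannot split evenly over two sites, so use the same site split for both needles within a participant where feasible.

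**Downsides.** Within one group the 5 v 5 period-adjusted test has less nominal power (smallest two-sided p = 2/252 = 0.008). Unequal carry-over should be assumed absent, and the assumption stated. It biases the device effect by half its size in the planned and the proposed analyses alike, but false positives can differ. With a carry-over of 0.2 SD and all 30 participants, the stratified period-adjusted test gives 14.4% against 7.5% for the pooled test at u=0.4, v=0. The order reverses at u=0.1, v=0.2 (7.2% against 20.7%).

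**Cost.** A rewording of Section 4, a clarification in Section 3.1, a line in Section 3.2 and a small constraint on the order of sites. No extra participants or insertions.
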